9.3.4.3 Patient Withdrawal

Patients may withdraw from the PER at any time at their own request. They may also be withdrawn at any time at the discretion of the HCP for administrative reasons. Note: discontinuation of lomitapide treatment is not a reason for withdrawal from the PER.

Patients who inform the CC or their HCP of their intent to prematurely withdraw from the PER will be asked a brief series of questions in an Exit Interview to determine the pregnancy status and to document the reason for withdrawal.

If the patient withdraws from the PER and also withdraws consent for disclosure of future information, no further assessments will be taken and no additional data will be collected beyond the Exit Interview. The PER may retain and continue to use any data collected before withdrawal of consent in accordance with the original patient consent form.

9.3.4.3.1 Losses to Follow-up

Multiple attempts (at least 4 attempts) to obtain information about the outcome of pregnancy will be made within 3 months following EDD before the patient is considered lost to follow-up. Similarly, multiple attempts will be made to obtain infant follow-up at 12 months after birth. The CC will contact the enroling HCP using multiple follow-up mechanisms (i.e., mail, fax, telephone, or e-mail) based on prior success and/or HCP preference to minimise the occurrence of missing data. In the US, if the CC is unable to solicit the outcome of the pregnancy or the infant status at 12 months from the HCP, the patient may be contacted for outcome information. In areas where it is possible to match against birth and death records, a final check will be made for comparison against vital statistics records.

9.4 Data Sources

As described in Section 8.3, the PER follows data collection strategies used in established population-based birth outcome registries. The below-listed variables will be collected; they include those in the FDA's Pediatric and Maternal Health Staff's (PMHS) Recommended Data Elements for Collecting Pregnancy Exposure Data, and additional variables specific to lomitapide use and HoFH medical history. Primary data collection will be accomplished via eCRFs completed by the CC staff. Medical records will be requested for all pregnancy outcomes and birth defects. Pregnancy outcomes and birth defects will be verified, whenever possible, by review of medical records.

Confidential Page 29 of 54

General

- Patient identifier or patient name and contact information where patient contact is possible
- Name of reporter at initial contact
- Date of initial contact
- Dates of any follow-up contacts
- Telephone number of reporter
- Additional contact names and phone numbers (if reporter is the patient)

Maternal Information

- Source of information (e.g., obstetrician, pregnant woman, other)
- Birth date
- Race
- Occupation
- Pre-pregnancy weight
- Maternal medical history (e.g., vaccination history, hypertension, diabetes, seizure disorder, thyroid disorder, allergic disorders, heart disease including congestive heart failure, connective disease, autoimmune disease, hepatitis, known risk factors for adverse pregnancy outcomes including environmental or occupational exposures, other).
- Obstetric History
 - Number of pregnancies and outcome of each (live birth, spontaneous abortion, induced abortion, ectopic pregnancy, molar pregnancy)
 - Previous maternal pregnancy complications
 - o Previous foetal/neonatal abnormalities and type
- Current Pregnancy
 - o Date of last menstrual period
 - Complications during pregnancy (including any adverse drug reactions such as reports of infection or fever) and dates
 - Number of foetuses
 - Labor/delivery complications

Confidential Page 30 of 54

- Disease course(s) during pregnancy and any complications
- Nursing history
- Exposure to radiation, pesticides and chemicals during pregnancy
- History of HoFH and method of diagnosis
- o Indication for lomitapide use
- Lomitapide treatment regimen (directly from patient whenever possible otherwise from HCP as reported by the patient)
 - Start date
 - Stop date
 - Duration of use
 - Changes in dose
 - Whether lomitapide was discontinued at the time of pregnancy identification
 - If not, changes in pattern of lomitapide use during pregnancy
- o Apheresis
- Other medical product exposures (prescription drugs, OTC products & dietary supplements) including contraceptive use
 - Name
 - Dosage & route
 - Date of first use & duration
 - Indication
- Recreational drug use (e.g., tobacco, alcohol, illicit drugs) and amount
- Family History (specify type, maternal/paternal, etc.):
 - Spontaneous abortions
 - Anomalies/malformations
 - Multiple foetuses/births
 - o Family history of HoFH and, if applicable, basis for diagnosis in parents
 - Other relevant family medical history

Confidential Page 31 of 54

Neonatal information

Initial

- o Source of information (e.g., obstetrician, paediatrician, mother)
- Date of receipt of information
- Date of birth or termination
- o Gestational age at birth or termination
- Gestational outcome (live born, foetal death/stillborn, spontaneous abortion, induced abortion)
- o Sex
- o Pregnancy weight gain of mother
- Obstetric complications (e.g., pre-eclampsia, premature labour, premature delivery)
- Pregnancy order (singleton, twin, triplet)
- o Results of neonatal physical examination including
 - Anomalies diagnosed at birth or termination
 - Anomalies diagnosed after birth (including age at diagnosis)
 - Weight at birth indicating whether small, appropriate, or large for gestational age
 - Length at birth
 - Condition at birth (including, when available, Apgar scores at 1 and 5 minutes, umbilical cord vessels and gases, need for resuscitation, admission to intensive care nursery)
 - Neonatal illnesses, hospitalizations, drug therapies

• Follow-up:

- o Source of information (e.g., paediatrician, mother)
- Date of receipt of information
- o Anomalies diagnosed since initial report (including age at diagnosis)
- Developmental assessment
- o Infant illnesses, hospitalizations, drug therapies

Confidential Page 32 of 54

9.4.1 Steering Committee

A Steering Committee will be established prior to initiation of the PER and will include clinicians and scientists with expertise in HoFH, obstetrics, teratology, paediatrics, epidemiology and biostatistics. Committee members will provide subject matter expertise for the program. The Steering Committee will adjudicate endpoints and be responsible for reviewing the data from the PER over time and making recommendations to the Sponsor regarding its conduct, and will assist in study interpretation.

9.5 Study Size

HoFH is an ultra-rare disease. The prevalence of defects in both alleles of the LDL-R (homozygous) has been calculated to occur in ∼1 in 1 million persons based on the estimated prevalence of 1 in 500 for the more common heterozygous FH, which is characterised by less severe hypercholesterolaemia.

Every attempt will be made to recruit eligible participants to this PER using methods found to be effective in similar pregnancy exposure registries. However, the number of women who will be candidates for inclusion with an eligible pregnancy cannot be accurately estimated.

Any pregnancies reported in previous clinical studies with HoFH or spontaneous or literature reports of pregnancies with known outcomes will be considered retrospective reports and will be included in the PER and analyzed separately. Any prospective pregnancies reported spontaneously (i.e., from patients not enrolled in the PER) will be handled by the Aegerion Safety Department or its designee. These reports will be included in a pooled analysis of all reports.

9.6 Data Management

9.6.1 Electronic Data Capture (EDC) System

The database will be housed at the CC on a physically and logically secure computer server maintained by the CC in accordance with written security policies. The EDC system meets approved established standards for the security of health information and is validated. The system also meets the International Committee on Harmonisation (ICH) guideline E6R1 regarding electronic study data handling and is available for audit upon request. The system is developed in accordance with a rigorous system development life cycle and quality program, which insures compliance with regulatory agency guidelines including 21 CFR Part 11 and HIPAA in the US and Annex 11 in the EU. Patient confidentiality will be strictly maintained.

Confidential Page 33 of 54

Patient identifying information will not be included in the clinical database, but must be maintained in a secure fashion by the physician. In countries where direct patient contact is possible, the CC will maintain the patient identifying data, including contact information, separately from the clinical data with limited access only by authorised study personnel.

Electronic CRFs (eCRFs) and correction documentation will be maintained in the EDC system's audit trail. System backups for data stored by the CC and record retention for the study data will be consistent with standard operating procedures.

The CC maintains high data quality standards and utilizes processes and procedures to repeatedly ensure that the data are as clean and as accurate as possible when presented for analysis. Data quality is enhanced through a series of programmed data quality checks that automatically detect and prevent the entry of out-of-range or anomalous data. A remote data quality audit will be performed at various times throughout the study on collected data.

9.6.2 Statistical Software

All analyses will be performed using SAS® for Windows statistical software (SAS Institute, Cary, NC) version 8.2 or higher using validated implementations of each application or SAS custom programming.

9.6.3 Data Entry

All data will be entered by the CC via a secure web-based EDC study database. All CC personnel will use secure usernames and passwords and will be fully trained in using the EDC system, including eCRF completion guidelines.

A data manager will perform concurrent review during the course of the data collection period. The data manager will generate ad-hoc queries for the CC to call HCPs when required. Further detail relating to data collection, processing, linking, protection, and reporting will be described in the Data Management Plan and/or Statistical Analysis Plan.

9.7 Data Analysis

Complete analytical specifications, including tables and listings, will be included in the Statistical Analysis Plan (SAP), which will be prepared separately. All statistical analyses will be coordinated by Aggerion or designee.

Confidential Page 34 of 54

Data will be presented for all patients enroled in the PER. An analysis of all PER participants combined will be provided. Separate analyses will also be conducted for prospective and retrospective reports. All data will be pooled for an additional analysis that includes spontaneous and literature reports from patients not participating in the PER. The proportion of pregnancies and births that have been lost to follow-up will also be calculated and reported. The primary outcome is major congenital abnormalities. Data will be presented using descriptive statistics using number and percent for categorical endpoints, n, mean, standard deviation (SD), standard error (SE) of mean, median, minimum (min), maximum (max) for continuous endpoints. The primary analyses will also present 95% confidence intervals (CI). Details of the analysis and table shells will be included in the SAP.

9.7.1 Potential Biases

As reporting of pregnancies will be totally voluntary, it is possible that even in prospectively reported pregnancies, potential bias could exist. For example, high-risk pregnancies may be more likely to be reported.

The calculation of risk of birth defects will exclude foetal losses (spontaneous abortions, induced abortions, or foetal deaths) for which no birth defects have been detected as they may introduce a classification bias. It is unknown what percentage of these pregnancies consists of potentially normal outcomes or birth defects. The PER will attempt to obtain information on birth defects detected at the time of foetal loss. However, the reporting HCP may not know the defect status of the aborted foetus. Evaluating spontaneous pregnancy losses is problematic for a number of reasons. First, the number of pregnancy losses in the general population is not well established. Early losses generally occur frequently and losses decrease as pregnancy progresses. Collecting information on pregnancy losses is difficult in this voluntary PER when enrolment time or initial contact with PER cannot be regulated. Spontaneous losses are likely to occur before the pregnancy is recognized. Even if the pregnancy is recognized, it may not be reported to the PER if the spontaneous loss occurred prior to PER enrolment.

Every effort will be made to obtain the outcome of every reported pregnancy. However, enroled patients for whom pregnancy outcome information is unobtainable will be considered lost to follow-up. It is possible that outcomes from pregnancies lost to follow-up could differ from those with documented outcomes. Because of differences in follow-up and reporting patterns, it is currently not possible to assess with any certainty what impact the potential biases of the loss to follow-up may have on the analysis. However, efforts at comparing some of the

Confidential Page 35 of 54

characteristics of each group will be conducted in an attempt to address this potential source of bias.

As lomitapide is indicated for individuals 18 years and older, data from females who become pregnant under the age of 18 will not be included; however, the number of excluded pregnant females will be reported in study reports.

9.7.2 Estimates of Incidence of Birth Defects

For the primary analysis, the incidence of birth defects reported to the PER is calculated by dividing the number of birth defects by the total number of live births. Pregnancy losses with reported birth defects at ≥20 gestation weeks are included in the numerator to increase sensitivity and to allow comparison with the US national population-based birth defect surveillance system (CDC MACDP) that uses this convention.

A secondary analysis, including pregnancy losses with reported birth defects occurring at <20 gestation weeks in the calculation of risk, will be conducted. The analysis of birth defects outcomes will be stratified by earliest trimester of exposure, maternal age, and other maternal risk factors, as appropriate. Statistical analysis will consider maternal age as it influences the rate of chromosomal abnormalities.

Ninety-five percent confidence intervals for birth defect rates will be calculated to assess the degrees of confidence. The prevalence in exposed pregnancies will be compared with the prevalence observed in the population-based birth defect data sources. The strength of evidence for lack of elevated levels of major birth defects in pregnancy exposures to lomitapide will be assessed by comparing the observed proportion of birth defects in the PER with rates from the external birth defect data sources, using a chi-square test.

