9.3.2.1 Major Birth Defects

Criteria for major birth defects will be those used in the MACDP. The MACDP defines a case as one having at least 1 major structural birth defect or syndrome. It uses a defect collection and coding system known commonly as "BPA" codes that was established by the British Paediatric Association (BPA), World Health Organization, and modified by the CDC (National Center for Birth Defects and Developmental Disabilities, 2004). The system is divided into "codable" and "conditional" defects. Codable defects are usually significant structural malformations or genetic syndromes. Additional details are provided in Annex 3.

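### The primary rate counts birth defects rather than affected outcomes, which conflicts with the MACDP case unit, and it is treated as a proportion although affected losses lie outside its denominator

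*Protocol*

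**What the plan says.** Section 9.7.2 defines the primary incidence as a ratio that "is calculated by dividing the number of birth defects by the total number of live births". It then widens the numerator: "Pregnancy losses with reported birth defects at ≥20 gestation weeks are included in the numerator". The reason given is "to allow comparison with the US national population-based birth defect surveillance system (CDC MACDP) that uses this convention". No matching change to the denominator is stated. A secondary analysis also brings in losses before 20 weeks with reported defects, without naming a denominator.

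The same section promises 95% confidence intervals and a formal comparison, "comparing the observed proportion of birth defects in the PER with rates from the external birth defect data sources, using a chi-square test".

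Section 9.3.2.1 fixes the outcome: "Criteria for major birth defects will be those used in the MACDP". It adds the unit that MACDP counts: "The MACDP defines a case as one having at least 1 major structural birth defect or syndrome".

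Section 9.7.1 says the risk calculation "will exclude foetal losses (spontaneous abortions, induced abortions, or foetal deaths) for which no birth defects have been detected". Section 9.5 says the number of eligible pregnancies cannot be estimated accurately, and Section 7 expects few.

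**The concern.** Two features of the primary ratio need attention, and they differ in weight.

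The first is the counting unit. The formula counts defects, whereas the external system counts outcomes with at least one defect. Several defects in one infant are not independent events. Counting them separately raises the estimate, and it also makes the data look like more independent events than there are. In a small registry a single infant with several malformations could then produce an apparent excess over MACDP that comes from the counting rule.

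The second is that the numerator is not contained in the denominator. An affected stillbirth adds an event but no trial. A binomial interval or a test on a proportion assumes that every event comes from the denominator, and here that need not be so.

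Both push the rate upwards. At stake are the primary estimate of a teratogenicity registry, its interval, and the only formal comparison in the protocol.

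**Working it through.** The protocol states no sample size, defect rate or power, so there is no figure of its own to reproduce. The check uses assumed counts and Clopper-Pearson 95% intervals. Both are illustrative choices; the protocol does not name an interval method.

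**Notation.** L = live births; s = affected losses at 20 weeks or later; C = affected outcomes (live-born or such losses), each counted once; D = total defects in those outcomes; m = D/C, the mean number of defects per affected outcome.

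- A = D/L: Section 9.7.2 as written
- B = C/L: MACDP case unit over live births
- K = C/(L + s): case unit with affected losses in the denominator

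**Step 1: counting unit.** A/B = D/C = m. Two defects per affected outcome double the rate and three triple it. With m = 1, A equals B and the problem vanishes.

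Smallest case, L = 10, one affected infant with 3 defects, no losses: A = 3/10 = 30% (6.7 to 65.2%); B = 1/10 = 10% (0.3 to 44.5%).

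With one affected loss (s = 1) and m = 3:

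| L | C | D | A | B | K |
|---|---|---|---|---|---|
| 20 | 2 | 6 | 6/20 = 30.0% (11.9 to 54.3) | 2/20 = 10.0% (1.2 to 31.7) | 2/21 = 9.5% (1.2 to 30.4) |
| 50 | 3 | 9 | 9/50 = 18.0% (8.6 to 31.4) | 3/50 = 6.0% (1.3 to 16.5) | 3/51 = 5.9% (1.2 to 16.2) |

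The intervals under A are computed as if each defect were an independent outcome, which is the distortion in question.

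**Step 2: effect on a comparison.** The documents give no background rate, so 2%, 3% and 5% are assumed. The one-sided binomial probability of r or more events in n = 20 is P(X ≥ r) = 1 − Σ(k<r) C(20,k) p^k (1−p)^(20−k). Two affected outcomes give r = 2 as cases, r = 4 with two defects each, and r = 6 with three each.

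| Assumed rate | r = 2 | r = 4 | r = 6 |
|---|---|---|---|
| 2% | 0.06 | 0.0006 | 0.000002 |
| 3% | 0.12 | 0.0027 | 0.00002 |
| 5% | 0.26 | 0.016 | 0.0003 |

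The same two affected outcomes move from unremarkable to an apparent strong excess through the counting rule alone. This is an exact tail used for illustration; the planned test is a chi-square.

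**Step 3: denominator.** B/K = (L + s)/L. With s = 1 this is 6/5 = 1.20 at L = 5, 21/20 = 1.05 at L = 20, 51/50 = 1.02 at L = 50, and 101/100 = 1.01 at L = 100. At L = 5 with two affected outcomes, one of them a loss, B = 2/5 = 40% and K = 2/6 = 33% (4.3 to 77.7%). The shift is well inside the sampling error.

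**Step 4: can the written ratio leave the range of a proportion?** Yes. With 3 live births (1 affected), 1 affected loss and 2 defects in each, A = 4/3 = 1.33, for which no binomial interval exists. With cases counted once, B = 2/3 and K = 2/4.

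**The case against.** The best reply on the counting unit is that the formula is shorthand. Section 9.3.2.1 adopts the MACDP criteria and case unit, the next sentence of Section 9.7.2 speaks of losses with defects (that is, of affected outcomes), and the section later calls the result a proportion. Section 9.7 leaves full specifications to the SAP, the Steering Committee adjudicates endpoints, and each pregnancy is to be described, so an infant with several defects would be visible. This makes it plausible that cases are meant. It does not remove the point: the protocol states the primary formula rather than deferring it, and no sentence in Section 9.7.2 says that each outcome counts once.

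On the denominator, the reply largely stands. Placing losses in the numerator only is a deliberate convention with a stated reason.

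Four stronger readings are tempting, and the documents do not support them:

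- A reader might infer that the live-birth denominator departs from MACDP. Section 9.7.2 says MACDP puts such losses in the numerator in the same way, and nothing in the protocol contradicts that. The departure from MACDP lies in the counting unit alone.
- A reader might infer that the secondary analysis can give absurd values, such as 200% from 2 affected early losses and 1 live birth. That assumes a live-birth denominator, which the protocol does not state for that analysis.
- A reader might infer that a loss examined and found normal must be counted as a non-case. Section 9.7.1 does exclude it. Including only examined losses, however, would select the denominator on who was examined, so this is a debatable choice and not an error.
- A reader might infer that the protocol prescribes an invalid binomial interval. It names no interval method.

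**Conclusion.** The point holds, mainly on the counting unit. As written, the primary formula conflicts with the case unit that Section 9.3.2.1 attributes to MACDP, and it inflates the rate by the mean number of defects per affected outcome: two-fold or three-fold for two or three defects, nothing if every affected outcome has one. The interval and the chi-square comparison are distorted accordingly.

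The denominator point holds in a limited form. The ratio is not a true proportion although Section 9.7.2 calls it one and tests it as one. The excess is only (L + s)/L, and it matters only when live births are very few, which this registry cannot rule out.

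The sizes rest on assumed counts, and the tail probabilities on assumed background rates of 2 to 5%. The direction and the multipliers do not depend on those rates. If the sponsor already intends to count cases, the correction is one of wording. It should be made before analysis, but it does not undermine the design.

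**What to change.** In Section 9.7.2, and in the SAP to match:

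1. Define the primary numerator as the number of live-born infants, or losses at 20 weeks or later, with at least one MACDP major defect, each counted once.
2. Keep live births as the denominator for the MACDP comparison, and label the result a ratio per live births rather than a proportion.
3. Add a sensitivity estimate: affected outcomes divided by live births plus the affected losses counted in the numerator. Use this version wherever a binomial interval or a test on a proportion is applied.
4. State the denominator of the secondary analysis, and apply the same rule when losses before 20 weeks are included.

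The cost is a wording change and one extra table line, with no new data. The downside is that the sensitivity estimate is not directly comparable with MACDP, so the two figures should be shown together and labelled clearly.

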6. MILESTONES

MILESTONE	PLANNED DATE		
Start of data collection	At time of first reported pregnancy after opening of the Lomitapide Observational Worldwide Evaluation Registry (LOWER)		
End of data collection	EU: Open Non-EU: At the closure of LOWER, which is planned for 01 March 2028 Note: any pregnancies that are on-going at the time of registry closure will be followed to outcome, with live births followed for an additional 12 months. Ongoing infant follow-up will be completed as well.		
Annual reports	Annually during the life of the PER		
Registration in the EU PAS register	To Be Determined		
Final report of study results	EU: Open Non-EU: 6 months after database lock (no later than 01 September 2028)		

Confidential Page 17 of 54

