9.3.4.2 PER Contact Schedule

In countries that allow contact with the patient and the HCP, during the course of the pregnancy the CC will contact the patient once per trimester. In countries with contact restricted to HCPs, during the course of the pregnancy the CC will contact the patient's HCP once per trimester.

Regardless of country of origin of the report, the patient's HCPs will be contacted at 6 to 7 months of gestation for the Prenatal Follow-Up and within 4 weeks after the EDD for Pregnancy Outcome Follow-Up. The infant's HCP will be contacted by the enroling HCP or by the CC when the infant is 12 weeks of age and at 12 months of age for paediatric follow-up.

The data collection schedule is outlined in Table 1 and Table 2.

Confidential Page 26 of 54

Table 1: Data Collection Schedule in Countries with Data Collection Restricted to HCPs

DATA COLLECTION	REGISTRATION BY LOMITAPIDE PRESCRIBER WITH CC	CC CONTACT WITH THE HCP AT EACH TRIMESTER	6 TO 7 MONTHS OF GESTATION FOR THE PRENATAL FOLLOW- UP	CC CONTACT WITH PRACTITIONER(S) AT THE PREGNANCY OUTCOME FOLLOW- UP WITHIN 4 WEEKS AFTER THE EDD	HCP OR CC CONTACT WITH THE INFANT'S HCP AT THE PAEDIATRIC FOLLOW-UP AT 12 WEEKS OLD AND 12 MONTHS OLD ¹
Consent	X				
Patient Demographics and Pregnancy History	X				
Lomitapide Use	X	X	X	X	X (if mother is nursing)
Concomitant Medications	X	X	X	X	X
Medical History	X				
Pregnancy Outcome				X	
Paediatric History and Examinations				X	X
Serious Adverse Events (Pregnancy-Related)		X	X	X	X

¹ The 12-week follow up should be conducted +/- one week.

Confidential Page 27 of 54

Table 2: Data Collection Schedule in Countries with Data Collection from Patients or HCPs

DATA COLLECTION	REGISTRATION/ ENROLMENT	CC CONTACT WITH THE PATIENT AT EACH TRIMESTER	CC CONTACT WITH THE PATIENT'S HCP(S) AT THE PRENATAL FOLLOW- UP, 6 TO 7 MONTHS OF GESTATION	CC CONTACT WITH THE HCP(S) AT THE PREGNANCY OUTCOME FOLLOW- UP ¹ WITHIN 4 WEEKS AFTER THE EDD	CC CONTACT WITH THE INFANT'S HCP AT THE PAEDIATRIC FOLLOW-UP AT 12 WEEKS AND 12 MONTHS OLD ^{2,3}
Consent ⁴	X				
Patient Demographics and Pregnancy History	X				
Contact Information	X	X	X		
Lomitapide Use	X	X	X	X	X (if mother is nursing)
Concomitant Medications	X	X	X	X	X
Medical History	X				
Pregnancy Status/ Outcome		X	X	X	
Paediatric History and Examinations				X	X
Serious Adverse Events (Pregnancy Related)		X	X	X	X

Confidential Page 28 of 54

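### The primary birth-defect rate has no ascertainment age: live births with pending or missing infant follow-up stay in the denominator but cannot add later-diagnosed defects

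*Protocol*

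**What the plan says.** Section 9.7.2 says that the primary incidence is "calculated by dividing the number of birth defects by the total number of live births". It adds that "Pregnancy losses with reported birth defects at ≥20 gestation weeks are included in the numerator". The rate is then compared with external population rates by a chi-square test.

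Defects are collected in stages. Section 9.3.4.2 has the infant's provider contacted "when the infant is 12 weeks of age and at 12 months of age for paediatric follow-up". Section 9.4 lists "Anomalies diagnosed at birth or termination" under the initial neonatal information, and a separate follow-up item, "Anomalies diagnosed since initial report (including age at diagnosis".

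On incomplete follow-up, Section 9.3.4.3.1 says that "multiple attempts will be made to obtain infant follow-up at 12 months after birth" but gives no consequence for the analysis if they fail. Section 9.7 reports the proportion of pregnancies and births lost. Section 9.7.1 discusses loss only where the pregnancy outcome itself cannot be obtained. Of losses without a detected defect, it says: "The calculation of risk of birth defects will exclude foetal losses".

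Section 6 plans reports "Annually during the life of the PER". It plans closure outside the EU for 01 March 2028, a further 12 months of follow-up for live births from pregnancies then ongoing, and a non-EU final report no later than 01 September 2028.

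**The concern.** The numerator can grow until an infant is 12 months old, but an infant enters the denominator at birth. At any data cut the rate therefore mixes infants observed for anything from 0 to 12 months. No section removes, separates or censors live births whose infant follow-up is pending or lost.

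Major congenital anomalies are the primary outcome, and Section 9.7.2 uses the rate to judge whether defects are not elevated. Section 7 describes the drug as teratogenic in rats and ferrets. A component that lowers the observed rate, by an amount that changes from one report to the next, weakens that use and makes successive annual rates hard to compare.

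The denominator is fixed in the protocol itself, so an analysis plan that follows it inherits the problem.

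**Working it through.** The protocol states no expected defect rate, loss rate or sample size, so there is no figure of its own to reproduce.

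**Inputs**
- From the protocol: the denominator is all live births (9.7.2); contacts are at outcome, 12 weeks and 12 months (9.3.4.2); reports are annual (6).
- Assumed: f, the share of live-birth defects found by the outcome report, is 0.5 to 0.9; q, the share of live births without completed infant follow-up, is 0.10 to 1; births are uniform over time; defect risk is unrelated to being lost.

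**Formula.** Infants with completed follow-up contribute all their defects, and the others contribute only the fraction f. So

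observed rate / 12-month rate = (1 - q) + qf = 1 - q(1 - f).

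| q | f = 0.5 | f = 0.7 | f = 0.9 |
|---|---|---|---|
| 0.10 | 0.950 | 0.970 | 0.990 |
| 0.25 | 0.875 | 0.925 | 0.975 |
| 0.50 | 0.750 | 0.850 | 0.950 |
| 1.00 | 0.500 | 0.700 | 0.900 |

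At q = 0.25 the relative understatement runs from 1 - 0.975 = 2.5% to 1 - 0.875 = 12.5%. If the true 12-month rate were 3% (illustration only), the observed rate would be about 2.6% to 2.9%.

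**Annual reports.** Infants born in the last 12 months cannot have had a 12-month visit. Counting years from the first birth, with no other loss, q = 1/k at year k. The ratio is:
- year 1 (q = 1): 0.50 to 0.90
- year 2 (q = 0.50): 0.75 to 0.95
- year 5 (q = 0.20): 0.90 to 0.98
- year 10 (q = 0.10): 0.95 to 0.99

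Counting instead from the first enrolment, at an assumed 8 weeks of gestation, birth comes 32 weeks later and the 12-month visit 84 weeks later. At week 104, q = 1 - (104 - 84)/(104 - 32) = 1 - 20/72 = 0.72. At week 260, q = 1 - 176/228 = 0.23. The timing shifts but the pattern does not.

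**Two qualifications to the formula.** An infant seen at 12 weeks but not at 12 months is partly ascertained, so treating that infant as not followed overstates the shortfall. Defects in losses at 20 weeks or later are known at the loss, so they dilute the relative effect on the whole rate.

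**Final report.** Infants born after about 01 September 2027 are under 12 months old on 01 September 2028. A pregnancy with its last menstrual period on the closure date, 01 March 2028, would deliver about 280 days later, in early December 2028. Its 12-month follow-up would end about December 2029. The final non-EU rate could therefore also rest on incomplete infants.

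**Check of possible remedies.** If numerator and denominator are both limited to infants with completed follow-up, the ratio is 1.00 under the same assumptions. If only unaffected infants with incomplete follow-up are dropped and every diagnosed case is kept, the ratio is (1 - q + fq)/(1 - q) = 1 + fq/(1 - q). At q = 0.25 that is 1 + 0.125/0.75 = 1.17 to 1 + 0.225/0.75 = 1.30, a larger error than the one being corrected.

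**The case against.** Several stronger readings are tempting, and the protocol does not support them.

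- A reader might infer that an infant without later follow-up is unobserved and simply counted as defect-free. Tables 1 and 2 schedule paediatric history and examinations at the outcome contact, and a defect seen then counts. Only later diagnoses are missed, so the shortfall is q(1 - f), not q.
- A reader might infer that the reported rate is biased low overall. The numerator includes defects from losses at 20 weeks or later that are not in the denominator, and Section 9.7.1 warns that high-risk pregnancies may be over-reported. Both push upward. The external sources' ascertainment window is not stated, so bias against them cannot be computed.
- A reader might see a contradiction with the exclusion of foetal losses in 9.7.1. That rule rests on defect status often being unknown after a loss, whereas live births have a planned neonatal examination. Different handling is defensible.

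It can also be said that the proportion of births lost is reported, that annual reports will describe age at diagnosis (Section 7), and that table layouts belong in the analysis plan. No section states that each annual report must compute the 9.7.2 rate. With few pregnancies expected, chance may dominate: an assumed 1 case in 20 live births has an exact 95% interval of about 0.1% to 25%.

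These points limit the size and certainty of the concern. They do not remove it. Disclosing losses leaves the rate unchanged, infants merely pending at a data cut are nowhere addressed, and a wide interval does not correct a denominator that mixes follow-up times.

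**Conclusion.** The point holds in a limited form. As written, the primary rate has no ascertainment age, and live births with pending or missing infant follow-up lower it relative to a 12-month rate by the factor 1 - q(1 - f). With f assumed at 0.5 to 0.9, the relative understatement is 2.5% to 12.5% at q = 0.25. It is largest in any early annual report that gives the rate, and shrinks to about 1% to 5% by year 10 if pending infants are the only cause.

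These figures rest on assumed f and q, uniform births, and loss unrelated to infant health. If sicker or healthier infants are lost selectively, the effect could be larger or smaller. Neither the net direction of the estimate nor its bias against the external rates can be concluded from the protocol.

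**What to change.** In Section 9.7.2, keep the all-live-births rate for comparison with the external convention and give it a stated ascertainment age. Report:

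- (a) defects diagnosed by the pregnancy-outcome contact, among all live births with an outcome report, with the existing rule for losses at 20 weeks or later unchanged;
- (b) as a companion analysis, defects diagnosed by 12 months, with numerator and denominator both restricted to infants with completed 12-month follow-up. State how an infant who dies before 12 months is counted.

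Beside each rate, in annual and final reports, show the number of infants pending and the number lost. State the ascertainment window of any external rate used for comparison. In Section 6, reconcile the closure date, the 12-month infant follow-up and the final-report date so that the final rate is not computed on incomplete infants.

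The cost is wording and a few table rows, using data already collected. The 12-month rate will have a smaller denominator and a wider interval, and it may be subject to selection if loss is related to infant health. That is why it belongs beside (a) and not in its place.
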